## 9.7 Efficacy Analyses

### 9.7.1 Primary Efficacy Endpoint

The primary efficacy endpoint is defined as the number of subjects who did not require an IV anesthetic drug (a 3rd line treatment) for SE treatment within the first 24 hours after study drug initiation.

The primary efficacy analysis will be conducted over the mITT Set. The primary efficacy analysis will be conducted by using a logistic model that includes treatment group as a factor along with factors controlling for age, GCS, and history of epilepsy. One-sided tests will be performed and compared to the critical values shown in Section 9.4, thus ensuring overall 1-sided Type I error  $\leq 0.025$ .

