The current therapies for SE have inherent risks, which must be balanced against the benefit of rapid seizure control. Benzodiazepines are the agents of choice for first line treatment of SE but their use can cause respiratory depression and hypotension, requiring the use of supportive therapies. Unfortunately, approximately 35-45% of patients are refractory to benzodiazepines. Second line therapy involves administration of an IVAED such as fosphenytoin, valproic acid, or levetiracetam for convulsive tonic-clonic status with the goal of stopping SE in patients who did not respond to first line treatment. When a patient with SE fails to respond to a benzodiazepine and the initial 2nd line therapy they are classified as having RSE. RSE develops in 31-44% of patients with SE, with a mortality of 16-39%. Additional therapeutic agents are required immediately; typically, anesthetics via continuous infusion. Currently, the recommended anesthetic drugs include midazolam, propofol, thiopental, and pentobarbital. Anesthetics are associated with risks, especially if administered for a long time – propofol infusion syndrome and hypotension are two recognized adverse events associated with anesthetics for SE treatment. In addition, the need for assisted ventilation and the management of hypotension and cardiopulmonary depression have their own risks.

Few therapies are approved for the treatment of SE and the urgent need for more efficacious therapies remains. Only two-thirds of patients in SE respond to first-line treatment. Resistance to treatment has been partially attributed to the internalization of post-synaptic GABAA-receptors and externalization of glutamate receptors. As prolonged epileptiform bursting results in a reduction of GABAA-mediated synaptic inhibition, antiepileptic treatments which rely on enhancing intra-synaptic GABAA neurotransmission become less effective the longer SE continues.

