### **9.3 Statistical Analysis Process**

The study will be analyzed by the sponsor or its agent.

The statistical analysis plan (SAP) will provide the statistical methods and definitions for the analysis of the efficacy and safety data, as well as describe the approaches to be taken for summarizing other study information, such as subject disposition, demographics, and baseline characteristics, study drug exposure, and prior and concomitant medications. The SAP will also include a description of how missing, unused, and spurious data will be addressed.

To preserve the integrity of the statistical analysis and study conclusions, the SAP will be finalized prior to database lock and the sponsor being unblinded to treatment assignments.

All statistical analyses will be performed using SAS® (SAS Institute, Cary, NC 27513). R (R Foundation for Statistical Computing) may be used for the predictive probability calculations used in the interim analyses.

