## 9.6 Study Population

The **Screened Set** will consist of all subjects who have signed an informed consent.

The **Safety Set** will consist of all subjects who have received ganaxolone IV solution.

The **Modified Intent-to-Treat (mITT) Set** includes all subjects who received at least one dose of the study drug and who provided any post study drug initiation seizure/status outcome data.

The **Per-Protocol Set** will consist of all subjects in the mITT population without major protocol violations. The Per Protocol population is for supportive efficacy analysis. Major protocol violations will be defined prior to database lock.

The **Completer Set** will consist of all subjects in the mITT who have completed the final scheduled primary assessment for the study.

The **Pharmacokinetic Set** will consist of all subjects in the Safety Set for whom the primary pharmacokinetic data is considered sufficient and interpretable.

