2.1 Primary Objective

- To establish that intravenous ganaxolone given concomitantly with 2nd line IV AED therapy is safe and effective in stopping status epilepticus that has already failed one 2nd line IV AED therapy and prevents escalation of treatment requiring an IV anesthetic drug (a 3rd line treatment) for seizure suppression.

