4 STATISTICAL METHODS

4.1 Analysis Populations

The Study populations will be defined as follows:

The **Screened Population** will consist of all subjects who have signed an informed consent.

The **Safety Population** will consist of all subjects who have received at least one dose of IV ganaxolone.

The **Pharmacokinetic Population** will consist of all subjects in the **Safety Population** for whom the primary pharmacokinetic data is available.

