4.4 General Analysis and Reporting Convention

Since data from only open-label phase are analyzed, there will be only one treatment group. For efficacy and safety summaries, where applicable, subjects will be categorized into three cohorts (Cohort 1: High, Cohort 2: Medium, and Cohort 3: Low) based upon target dose of study medication. An overall group will also be reported representing all subjects.

General Convention:

The following are general conventions for the analysis of study data. If alternative methods are present in the specific evaluation sections of this SAP, those conventions will take precedence over these general conventions.

- Continuous study measurements will be summarized by treatment group (Open-Label Group or Cohorts and Open-Label Group) and time point (as applicable) using descriptive statistics (n, mean, standard deviation, median, minimum, and maximum). Means and medians will be presented with one more decimal place than the precision of the data. Standard deviations will be presented with two more decimal places than the precision of the data. Minimums and maximums will be presented with the same precision as the original data.

- Categorical study assessments will be summarized by treatment group (Open-Label Group or Cohorts and Open-Label Group) and time point (as applicable) using frequency counts and percentages. Unless stated otherwise, percentages are based on the number of subjects in the treatment group of the analysis set. Percentages will be presented with one decimal place (xx.x), with the exception of 100%, which will be displayed without any decimal places.
- Descriptive summaries based on the modified ITT (mITT) analysis set and per-protocol (PP) analysis set will be displayed by randomized treatment.
- Descriptive summaries based on the safety analysis set will be displayed by actual treatment received.
- All listings will be listed by cohort, subject, and time point (if applicable).
- Scheduled assessments will be included in summaries. Unscheduled assessments will only be included in the display sections that report abnormal laboratory, vitals, or ECG values. Data from all assessments (scheduled and unscheduled), will be included in listings.
- All statistical tests will be performed at a significance level of 0.05 (two-tailed). Where applicable, two-sided 95% confidence intervals will be reported. For tables.

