4.8 Efficacy Analyses

All efficacy analyses will be conducted for the Safety Population.

Considering that data from only open-label phase is available for analysis, efficacy assessments are only summarized and listed. There will be no statistical inferential test of any efficacy endpoint.

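### The primary endpoint has no scoring rule for death before 24 hours, so on its plain reading a dosed subject who dies without an IV anesthetic counts as a success

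*Protocol*

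**What the plan says.** SAP 4.2.1 is the operative text, because SAP section 1 states that the SAP overrides the protocol's statistics where the two differ substantially. Its wording matches protocol 9.7.1: "The primary efficacy endpoint is defined as the number of subjects who did not require an IV anesthetic drug", with the need limited to treatment of SE and to the first 24 hours after study drug initiation. No second condition is attached.

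The set to which this applies is fixed in three places in the SAP:

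- Section 4.8: "All efficacy analyses will be conducted for the Safety Population".
- Section 4.1: that population "will consist of all subjects who have received at least one dose of IV ganaxolone".
- Section 4.4: unless stated otherwise, "percentages are based on the number of subjects in the treatment group of the analysis set".

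The objective in SAP 2.1 is to show that the drug "is safe and effective in stopping status epilepticus that has already failed one 2nd line IV AED therapy and prevents escalation of treatment" to an IV anesthetic.

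On missing outcomes, protocol 9.3 hands the matter on: "The SAP will also include a description of how missing, unused, and spurious data will be addressed". The SAP rules that follow (section 4.4) impute dates of adverse events and medications only.

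**The concern.** A subject can fail to meet the objective and still satisfy the endpoint. Someone who is dosed, dies at hour 10, say, and never reaches an IV anesthetic has not had treatment escalated, but has not had a good outcome either. With no survival condition and every dosed subject in the denominator, that subject enters the numerator. The error runs in one direction: it can raise the reported success rate or leave it alone, and cannot lower it.

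A smaller gap sits beside it. If a subject leaves the study before 24 hours and it is not known whether an anesthetic was needed, the documents do not say whether that is success, failure or exclusion. The choice falls to whoever programs the table.

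At stake is the main efficacy figure of a small single-arm group, reported overall and for three dose cohorts. No hypothesis test depends on it.

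**Working it through.** The plan gives no figure for deaths or unknown status before 24 hours, so there is no number to reproduce. The check is first a reading of the text, then the effect per subject.

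**Step 1. Does any other provision score an early death?**

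| Provision | What it does | Does it score the death? |
|---|---|---|
| Protocol 4.2, exclusions 1, 2, 10 and 12 (short life expectancy, anoxic injury, care agreements that bar standard SE treatment, investigator-judged undue risk) | Make early death without an anesthetic less likely | No |
| Protocol 9.6, mITT Set: dosed subjects "who provided any post study drug initiation seizure/status outcome data" | One SE or seizure record after initiation keeps a subject in | No; and the SAP uses the Safety Population instead |
| Protocol 9.7.2 and SAP 4.2.2, mortality as a secondary endpoint | Reports deaths separately | No |
| SAP 4.9.1 (deaths) and 4.5 (disposition) | List and summarize deaths and discontinuation reasons | No |
| SAP 4.8.1 to 4.8.7 | Describe the individual efficacy summaries | No; none derives the primary endpoint, although SAP 5.1 says it was summarized |

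None of these takes an early death out of the numerator.

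**Step 2. Does any provision score unknown status?** Date imputation does not turn an unknown 24-hour status into success or failure. The section 4.4 percentage convention fixes the denominator, not the score. Protocol 3.1 lets subjects who terminate early for operational reasons be replaced, but a replaced subject who was dosed stays in the Safety Population.

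**Step 3. Effect of one early death.** Moving one subject from success to non-response changes the rate by 100/n percentage points.

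- n = 30 (planned maximum, protocol synopsis): 100/30 = 3.3
- n = 20 (assumed): 100/20 = 5.0
- n = 10 (assumed: 30 subjects split equally over three cohorts): 100/10 = 10.0

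For example, suppose 21 of 30 are counted as successes and one of them died before 24 hours. As written the rate is 21/30 = 70.0%; with the death as non-response it is 20/30 = 66.7%.

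**Step 4. Effect of one unknown status.** Assume 21 known successes, 8 known failures and 1 unknown among 30.

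- Unknown as non-response: 21/30 = 70.0%
- Unknown excluded: 21/29 = 72.4%
- Unknown as success: 22/30 = 73.3%

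The spread is 3.3 points, and the plan does not say which figure is meant.

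**The case against.** Four points can be made on the other side.

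*The wording may not mean this.* The endpoint speaks of subjects who did not *require* an anesthetic, not of those who did not *receive* one. A subject who dies in uncontrolled SE may be said to have required one. The ambiguity is genuine, but the SAP neither adopts that reading nor names who would judge the need in a subject who was never given the drug. It would also leave open a death from another cause after SE had stopped.

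*Such cases should be uncommon.* Exclusion 10 matters most, because it closes an obvious route to dying without an anesthetic: a limit on care already in place at entry. Limits agreed after entry remain possible. The exclusions reduce the likelihood and do not supply a rule. This point stands as to size.

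*Unknown status is nearly hypothetical.* Treatment is inpatient, protocol 5.2 collects all concomitant medications through the in-patient follow-up day, and protocol 4.5 keeps subjects who stop study drug in follow-up. What is left is mainly withdrawal of consent. This stands: alone, the unknown-status gap would be little more than missing detail.

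*The consequence is limited and visible.* There is no inferential test, and deaths, discontinuations and anesthetics are all listed, so a careful reader could find an affected subject. That is a fair limit on severity, but the headline rate should not need correcting from the listings.

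Three stronger readings are tempting and not supported. First, a reader might take the protocol's background statement that "RSE develops in 31-44% of patients with SE, with a mortality of 16-39" per cent and infer that many subjects are affected. That is mortality over the whole course, cited from elsewhere; neither document says what share of deaths falls before 24 hours, still less without an anesthetic. Second, a reader might infer harm to the 85% power or to the Type I error. Those belong to the double-blind comparison, which the SAP says will be a separate phase 3 study. Third, a reader might infer that the endpoint itself is wrong because it does not measure SE cessation. The amendment history in protocol Appendix 2 shows that the focus on IV anesthetics was deliberate, and this point does not dispute it.

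**Conclusion.** The concern holds, within limits. On its plain reading the primary endpoint counts a dosed subject who dies before 24 hours without an IV anesthetic as a success, and nothing elsewhere in the protocol or SAP corrects this. The resulting bias is zero or upward.

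The total effect cannot be stated, because neither the number of such subjects nor the final sample size is in the documents; if no such death occurred, it is nil. The supported figure is the effect per subject: 3.3 points overall at the planned maximum of about 30, and more in a dose cohort (10.0 points only if cohorts of 10 are assumed). The 21-responder examples are illustrations.

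Because the SAP plans summaries without tests, the consequence is a misstated descriptive primary rate, overall and by cohort. The omission is worth correcting because it affects the study's main efficacy figure and is cheap to repair. The rule for early death carries most of the weight; the rule for unknown status is a completion of it.

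**What to change.** In SAP 4.2.1, keep the anesthetic-based endpoint as worded and add: *Death before 24 h is non-response. A subject whose anesthetic status to 24 h is unknown is counted as non-response, with all dosed subjects in the denominator.*

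Then:

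- report the number of subjects classified under each part of the rule, by cohort and overall, and list them;
- add one sensitivity summary that excludes subjects who terminated for operational reasons, since non-response is a conservative score for them;
- label the rule post hoc if it is set after the data were seen. SAP section 5.1 is written partly in the past tense, so this may apply.

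The cost is two sentences, one extra table and one listing. The source data for deaths, disposition and anesthetics are already planned outputs under SAP 4.9.1, 4.5 and 4.9.3. Relative to counting these subjects as successes, the reported rate can only stay the same or fall.

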### 9.7.2 Secondary Endpoints

- For subjects on concomitant second-line therapy: time to cessation of SE or next treatment decision (defined as the need for an IV anesthetic drug (a 3rd line treatment) when on ganaxolone)
- Level of responsiveness as assessed by the GCS, Four Score Scale, and RASS at 24 hours post study drug initiation
- The number of subjects who did not require additional 2nd line IV AED therapy for SE treatment in the 24-hours after taper
- Safety and tolerability of ganaxolone IV solution as adjunctive SE therapy as assessed by neurologic, EEG, and physical examinations, clinical laboratory tests, ECGs, vital signs, and spontaneously reported AEs
- Number of subjects who maintained SE resolution 24 hours after study drug taper and at Week 4
- Number of subjects with seizure(s) following cessation of SE through the in-patient follow-up day
- Level of responsiveness as assessed by the GCS if SE is continuing, on the in-patient follow-up day
- Seizure burden assessed as duration of electrographic seizure activity per hour of EEG recording collected
- Clinical outcome as assessed by MRS at the in-patient follow-up day and Week 4
- Characterization of the pharmacokinetic profile of ganaxolone IV solution in SE subjects
- Length of stay in intensive care unit and hospital, mortality, morbidity, need for and duration of intubation and mechanical ventilation, and seizure freedom

### 9.7.3 Exploratory Endpoints

- [REDACTED]
- [REDACTED]
- [REDACTED]
- [REDACTED]
- [REDACTED]

### 9.8 Safety Analyses

AEs will be coded using the Medical Dictionary for Regulatory Activities. The number of events, incidence, and percentage of treatment-emergent AEs will be calculated overall, by system organ class, by preferred term, and by treatment group. Treatment-emergent AEs will be further summarized by severity and relationship to study drug. AEs related to study drug, AEs leading to withdrawal, SAEs, and deaths will be similarly summarized and listed.

Clinical laboratory tests, vital signs, ECG findings, MRS, and FOUR Score will be summarized by treatment group and visit. Potentially clinically important findings will also be summarized or listed. Where applicable, the estimated subject mortality will be calculated using APACHE or APACHE 2 score.

The study team physician and the clinical operations lead will monitor emerging safety data from each subject periodically throughout the duration of the study. This data will be blinded for the double-blind group.

### 9.9 Other Analyses

EEGs will be monitored and assessed by the site for the following:

- EEG pattern consistent with SE
- EEG pattern consistent with cessation of SE
- Seizure burden
- Burst suppression (if achieved)

A central EEG reader will verify site-marked EEG patterns to confirm consistency of SE and seizure identification and cessation.

Blood samples for neurosteroid levels will be analyzed by a bioanalytical laboratory. Details of the data analysis and presentation will be detailed in the statistical analysis plan.

Cerebral spinal fluid, if collected per the investigator's discretion and adequate volume is available, will be stored for future analysis.

### **9.9.1 Pharmacokinetic Analyses**

The pharmacokinetic population includes all subjects who have received at least 1 dose of study drug and who have sufficiently complete concentration-time data (at least 5 data points with a quantifiable plasma ganaxolone concentration value).

The following ganaxolone plasma pharmacokinetic parameters will be calculated as data allows and as appropriate using noncompartmental approaches. Pharmacokinetic variables will be computed using WinNonlin Professional, version 5.2 or similar software. Actual elapsed sampling times relative to ganaxolone administration will be used for the estimation of pharmacokinetic metrics. The following pharmacokinetic parameters of ganaxolone in plasma will be calculated. Additional parameters may be calculated on discretion of the pharmacokineticist, pending review of the data.

- Maximum plasma concentration ( $C_{max}$ )
- Time of maximum concentration ( $T_{max}$ )
- Area under the concentration versus time curve from time 0 to  $t$  hours ( $AUC_{0-t}$ )
- Area under the concentration versus time curve from time 0 to infinity ( $AUC_{inf}$ )
- Clearance (CL). Calculated as dose/ $AUC_{inf}$

## **10. SPONSOR'S AND INVESTIGATOR'S RESPONSIBILITIES**

This study is conducted in accordance with current applicable regulations, International Conference on Harmonisation (ICH), European Union (EU) Directive 2001/20/EC and its updates, and local ethical and legal requirements.

The name and address of each third-party vendor (e.g., CRO) used in this study will be maintained in the investigator's and sponsor's files, as appropriate.

### **10.1 Sponsor's Responsibilities**

#### **10.1.1 Good Clinical Practice (GCP) Compliance**

The study sponsor and any third party to whom aspects of the study management or monitoring have been delegated will undertake their assigned roles for this study in compliance with all applicable industry regulations, ICH GCP Guideline E6 (1996), and EU Directive 2001/20/EC, as well as all applicable national and local laws and regulations.

Visits to sites are conducted by representatives of the study sponsor and/or the company organizing/managing the research on behalf of the sponsor to inspect study data, subjects' medical records, and eCRFs in accordance with current GCP and the respective local and

(inter)national government regulations and guidelines. Records and data may additionally be reviewed by auditors or by regulatory authorities.

The sponsor ensures that local regulatory authority requirements are met before the start of the study. The sponsor (or a nominated designee) is responsible for the preparation, submission, and confirmation of receipt of any regulatory authority approvals required prior to release of study drug for shipment to the site.

#### **10.1.2 Public Posting of Study Information**

The sponsor, or their designee, is responsible for posting appropriate study information on applicable websites such as ClinicalTrials.gov. Information included in clinical study registries may include participating investigator's names and contact information.

#### **10.1.3 Submission of Summary of Clinical Study Report to Competent Authorities of Member States Concerned and Ethics Committees**

The sponsor will provide a summary of the clinical study report to the competent authority of the member state(s) concerned as required by regulatory requirement(s) and to comply with the Community guideline on GCP. This requirement will be fulfilled within 6 months of the study completion date for pediatric studies and within 1 year for non-pediatric studies as per guidance.

